9.1.3 End of Study

Subjects will end the study once contacted by the site by phone call at week 52.

Completion of the study is defined as the last day that protocol-specified procedures are conducted for an individual subject. Subjects who are not deceased, have not

Approved

withdrawn consent, or are not lost to follow-up, should have at minimum an EOS assessment for vital status (alive or deceased) and adverse events.

9.2 Description of General Study Assessments and Procedures

The sections below provide a description of the individual study procedures for required time points.

9.2.1 General Assessments

9.2.1.1 Informed Consent

All subjects or their legally authorized representative must sign and personally date the IRB/IEC approved informed consent before any study-specific procedures are performed.

9.2.1.2 Demographics

Demographic data collection including sex, age, race, and ethnicity will be collected in order to study their possible association with subject safety and treatment effectiveness.

9.2.1.3 Medical History

The investigator or designee will collect a targeted medical and surgical history on the following conditions or indications that started prior to study entry/screening through the start of the adverse event reporting period: cardiovascular disease. Record all findings on the medical history CRF. The current severity will be collected for each condition that has not resolved. Additionally, patient reported cardiovascular risk factors will be collected at the time of randomization.

9.2.1.4 Physical Examination

Physical examination will be performed as per standard of care. Physical examination findings should be recorded on the appropriate CRF (eg, medical history, event).

9.2.1.5 Physical Measurements

9.2.1.5.1 Height

Height in centimeters should be measured without shoes.

9.2.1.5.2 Weight

Weight in kilograms should be measured without shoes.

9.2.2 Efficacy Assessments

Disease assessments will be based on intracoronary imaging (OCT and IVUS) and LDL-C assessments at scheduled timepoints in the Schedule of Activities ([Table 2-1](#)).

Approved

9.2.2.1 Intracoronary Imaging (OCT and IVUS)

In order to minimize the chances of performing unnecessary invasive procedures, investigators should ensure that subjects' initial screening LDL-C results are available prior to performing the baseline OCT and IVUS examination. Thereafter, subjects will undergo clinically-indicated coronary angiography for further clinical evaluation following their hospitalization for NSTEMI-ACS. If angiographic criteria are met, the subject will have baseline OCT and IVUS completed. Subjects who require a PCI deemed necessary by the qualifying angiogram will have baseline OCT and IVUS imaging performed immediately following the PCI. OCT and IVUS must not be performed in vessels that underwent an intervention.

The accuracy and reproducibility of the imaging endpoints of the study are dependent upon Investigator's commitment to rigorous image acquisition techniques. The central imaging core laboratory will provide a separate imaging guidance document to all participating sites. Adherence to these guidelines will ensure low inter- and intra-observer variability and high image quality.

For each patient, all imaging conditions at baseline must be duplicated at follow-up utilizing the same imaging system. The OCT and IVUS systems must not be changed between the baseline and follow-up examinations. All baseline studies (angiography, OCT, IVUS) must be forwarded to the imaging core laboratory for informational review. OCT images must be reviewed and approved by the imaging core laboratory before subjects return for randomization visit.

9.2.2.2 LDL-C

Low-density lipoprotein cholesterol analysis will be performed by local laboratory assessments during the Screening period. The results will have to be recorded in CRF. Treatment period LDL-C analysis will be performed by the central laboratory. The blood samples will be drawn at the time points indicated in the Schedule of Activities ([Table 2-1](#)).

9.2.3 Safety Assessments

Planned time points for all safety assessments are listed in the Schedule of Activities ([Table 2-1](#)).

Approved

9.2.3.1 Adverse Events

9.2.3.1.1 Time Period and Frequency for Collecting and Reporting Safety Event Information

9.2.3.1.1.1 Adverse Events

The adverse event grading scale to be used for this study will be the Common Terminology Criteria for Adverse Events (CTCAE) or the Amgen Adverse Event Grading Scale and is described in [Appendix 4](#).

The investigator is responsible for ensuring that all adverse events observed by the investigator or reported by the subject that occur after signing the informed consent through the EOS are reported using the Event CRF.

9.2.3.1.1.2 Serious Adverse Events

The investigator is responsible for ensuring that all serious adverse events observed by the investigator or reported by the subject that occur after signing the informed consent through 30 days after the last dose of investigational product or EOS (whichever is later) are reported using the Event CRF.

All serious adverse events will be collected, recorded, and reported to the sponsor or designee within 24 hours, as indicated in [Appendix 4](#). The investigator will submit any updated serious adverse event data to the sponsor within 24 hours of it being available.

The criteria for grade 4 in the CTCAE grading scale differs from the regulatory criteria for serious adverse events. It is left to the investigator's judgment to report these grade 4 abnormalities as serious adverse events.

9.2.3.1.1.3 Serious Adverse Events After the Protocol-required Reporting Period

There is no requirement to monitor study subjects for serious adverse events following the protocol-required reporting period or after EOS. However, these serious adverse events can be reported to Amgen. Per local requirements in some countries, investigators are required to report serious adverse events that they become aware of after EOS. If serious adverse events are reported, the investigator is to report them to Amgen within 24 hours following the investigator's knowledge of the event.

Serious adverse events reported outside of the protocol-required reporting period will be captured within the safety database as clinical trial cases and handled accordingly based on relationship to investigational product.

Approved

The method of recording, evaluating, and assessing causality of adverse events, adverse device effects, and serious adverse events and the procedures for completing and transmitting serious adverse event reports are provided in [Appendix 4](#).

9.2.3.1.2 Method of Detecting Adverse Events and Serious Adverse Events

Care will be taken not to introduce bias when detecting adverse events and/or serious adverse events. Open-ended and non-leading verbal questioning of the subject is the preferred method to inquire about adverse event occurrence.

9.2.3.1.3 Follow-up of Adverse Events and Serious Adverse Events

After the initial adverse event/serious adverse event report, the investigator is required to proactively follow each subject at subsequent visits/contacts. All adverse events and serious adverse events will be followed until resolution, stabilization, until the event is otherwise explained, or the subject is lost to follow-up (as defined in [Section 8.3](#)).

Further information on follow-up procedures is given in [Appendix 4](#).

All new information for previously reported serious adverse events must be sent to Amgen within 24 hours following knowledge of the new information. If specifically requested, the investigator may need to provide additional follow-up information, such as discharge summaries, medical records, or extracts from the medical records. Information provided about the serious adverse event must be consistent with that recorded on the Event CRF.

9.2.3.1.4 Regulatory Reporting Requirements for Serious Adverse Events

If subject is permanently withdrawn from protocol-required therapies because of a serious adverse event, this information must be submitted to Amgen.

Prompt notification by the investigator to the sponsor of serious adverse events is essential so that legal obligations and ethical responsibilities towards the safety of subjects and the safety of a study treatment under clinical investigation are met.

The sponsor has a legal responsibility to notify both the local regulatory authority and other regulatory agencies about the safety of a study treatment under clinical investigation. The sponsor will comply with country-specific regulatory requirements relating to safety reporting to the regulatory authority, IRBs/IECs, and investigators.

Individual safety reports must be prepared for suspected unexpected serious adverse reactions (SUSAR) according to local regulatory requirements and sponsor policy and forwarded to investigators as necessary.

Approved

An investigator who receives an individual safety report describing a serious adverse event or other specific safety information (eg, summary or listing of serious adverse events) from the sponsor will file it along with the Investigator's Brochure and will notify the IRB/IEC, if appropriate according to local requirements.

To comply with worldwide reporting regulations for serious adverse events, the treatment assignment of subjects who develop serious, unexpected, and related adverse events may be unblinded by Amgen before submission to regulatory authorities. Aggregate analyses may also be unblinded by the Safety Assessment Team (SAT) as appropriate. Investigators will receive notification of related serious adverse events reports sent to regulatory authorities in accordance with local requirements.

9.2.3.1.5 Pregnancy and Lactation

Details of all pregnancies and/or lactation in female subjects and, if indicated, female partners of male subjects will be collected after the start of study treatment and until 15 weeks after the last dose of investigational product.

If a pregnancy is reported, the investigator is to inform Amgen within 24 hours of learning of the pregnancy and/or lactation and is to follow the procedures outlined in [Appendix 5](#). Amgen Global Patient Safety will follow-up with the investigator regarding additional information that may be requested.

Abnormal pregnancy outcomes (eg, spontaneous abortion, fetal death, stillbirth, congenital anomalies, ectopic pregnancy) are considered serious adverse events.

Further details regarding pregnancy and lactation are provided in [Appendix 5](#).

9.2.3.1.6 Adverse Device Effects

In order to fulfill regulatory reporting obligations worldwide, the investigator is responsible for the detection and documentation of any adverse device effects that occur during the study with such devices.

An adverse device effect is any adverse event related to the use of a combination product or medical device. Adverse device effects include adverse events resulting from insufficient or inadequate IFU, adverse events resulting from any malfunction of the device, or adverse events resulting from use error or from intentional misuse of the device.

All adverse device effects are to be reported as adverse events following the same reporting periods and procedures.

Approved

Product complaints are described in [Section 7.1.6](#).

Further details regarding adverse device effects can be found in [Appendix 4](#).

9.2.3.2 Vital Signs

The following measurements must be performed: systolic/diastolic blood pressure and heart rate. Subject must be in a supine position in a rested and calm state for at least 5 minutes before blood pressure assessments are conducted. If the subject is unable to be in the supine position, the subject should be in most recumbent position as possible. The position selected for a subject should be the same that is used throughout the study and documented on the vital sign CRF. Record all measurements on the vital signs CRF.

9.2.3.3 Vital Status

Vital status must be obtained for all subjects within the limits of local law. This includes subjects who may have discontinued study visits with or without withdrawing consent and should include interrogation of public databases, if necessary. If deceased, the date and reported cause of death should be obtained.

9.2.4 Clinical Laboratory Assessments

Refer to [Appendix 2](#) for the list of clinical laboratory tests to be performed and to the Schedule of Activities ([Table 2-1](#)) for the timing and frequency.

The investigator is responsible for reviewing laboratory test results and recording any clinically relevant changes occurring during the study in the Event CRF. The investigator must determine whether an abnormal value in an individual study subject represents a clinically significant change from the subject's baseline values. In general, abnormal laboratory findings without clinical significance (based on the investigator's judgment) are not to be recorded as adverse events. However, laboratory value changes that require treatment or adjustment in current therapy are considered adverse events. Where applicable, clinical sequelae (not the laboratory abnormality) are to be recorded as the adverse event.

All protocol-required laboratory assessments, as defined in [Appendix 2](#), must be conducted in accordance with the laboratory manual and the Schedule of Activities ([Table 2-1](#)).

Laboratory/analyte results that could unblind the study should not be performed during the subject's participation in the study. Central laboratory results of the lipid testing will be blinded post-treatment until unblinding of the clinical database and will not be

reported to the investigator post-screening. In addition, investigators and staff involved with this trial and all medical staff involved in the subject's medical care should refrain from obtaining lipid panels between randomization and at least 12 weeks after the subject ends the study (to avoid potential unblinding).

9.2.4.1 Pregnancy Testing

A high sensitive (urine or serum) pregnancy test should be completed at screening and within 7 days of initiation of investigational product for females of childbearing potential.

Note: Females who have undergone a bilateral tubal ligation/occlusion should have pregnancy testing per protocol requirements. (If a female subject, or the partner of a male subject, becomes pregnant it must be reported on the Pregnancy Notification Worksheet, see [Figure 12-2](#)). Refer to [Appendix 5](#) for contraceptive requirements.

An additional pregnancy test should be performed also at week 24 and week 50.

Additional on-treatment pregnancy testing may be performed at the investigator's discretion or as required per local laws and regulations.

9.2.5 Biomarker Development

Biomarkers are objectively measured and evaluated indicators of normal biologic processes, pathogenic processes, or pharmacologic responses to a therapeutic intervention.

Biomarker development can be useful in developing markers to identify disease subtypes, guide therapy, and/or predict disease severity.

Amgen may attempt to develop test(s) designed to identify subjects most likely to respond positively or negatively to evolocumab to investigate and further understand cardiovascular disease.

Blood samples are to be collected for biomarker development at the time points specified in the Schedule of Activities ([Table 2-1](#)).

10. Statistical Considerations

10.1 Sample Size Determination

The planned total sample size is 150 subjects (75 randomized to evolocumab 420 mg SC QM and 75 randomized to placebo SC QM). This sample size will provide sufficient power (90%) to determine whether there is a treatment effect of evolocumab relative to placebo in the primary endpoint.

Approved

The assumptions in the sample size calculation are based on a linear regression meta-analysis of 7 historical trials (Dai et al, 2017; Hou et al, 2016; Kataoka et al, 2014; Komukai et al, 2014; Nishio et al, 2014; Hattori et al, 2012; Takarada et al, 2009) weighted by sample sizes.

The analysis result indicates that every 1 mg/dL reduction in LDL-C is estimated to be associated with 1.4785 μm increase in FCT in 12-month follow-up. Assuming a 50 mg/dL reduction in LDL-C, the predicted mean increase (95% CI) in FCT from the meta-analysis was 73.92 (50.97, 96.88) μm . For this study, the assumed treatment effect is at least 50.97 μm increase in FCT, which is approximated from the lower bound 95% CI of the expected change in FCT from the regression model, based on a conservative assumption of 50 mg/dL reduction in LDL-C from baseline to week 50.

The SD of FCT measurement at baseline or at the end of various length of follow-up was reported in a wide range (10.6 to 124 μm) based on 15 to 134 subjects per arm in the historical trials. The SD of change in FCT was only reported in 2 of the 7 trials, ranging from 22 to 86 μm . The assumed common SD for this study is 86 μm to be conservative.

Assuming 1 out of 6 subjects will not complete both baseline and week 50 OCT assessments, and therefore be excluded in the primary analysis, the sample size of 150 subjects will provide approximately 125 subjects in the primary analysis to ensure 90% power to test the study hypothesis.

The sample size calculation was performed using a 2-sided t-test with a 0.05 significance level. The sample size calculation was derived using East[®] software (version 6.4).

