3.1 Study Rationale

Plaque morphology plays pivotal role for the development of acute coronary syndromes (ACS) ([Toutouzas et al, 2011](#); [Ino et al, 2011](#)). Lipid-lowering therapy with statins has proven to have beneficial effects on plaque morphology in patients suffering from coronary artery disease (CAD) ([Takarada et al, 2009](#)). Treatment with evolocumab in addition to optimal statin therapy has been shown to result in a regression of atherosclerotic plaque burden ([Nicholls et al, 2016](#)). While treatment with evolocumab is associated with a reduction in cardiovascular events ([Sabatine et al, 2017](#)), it is uncertain whether additional effects on plaque, beyond regression, may contribute to this benefit. The development of advanced imaging techniques permits evaluation of the effect of treatment on plaque phenotype features consistent with plaque instability. This study seeks to identify morphologic changes, such as increase in fibrous cap thickness (FCT), in atherosclerotic plaques associated with treatment with evolocumab and maximally tolerated statin therapy with or without additional lipid-modifying medication in patients presenting with non-ST-segment elevation (NSTEMI)-ACS using optical coherence tomography (OCT; primary, secondary, and exploratory endpoints) and intravascular ultrasound (IVUS; exploratory endpoints only - see [Section 4.1](#)).

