
• To evaluate the effects of evolocumab on lipid parameters in subjects with NSTEMI-ACS who are taking maximally tolerated statin therapy.• To evaluate the effects of evolocumab on features of coronary plaques in subjects with NSTEMI-ACS who are taking maximally tolerated statin therapy using different imaging techniques.	
• Absolute and percent changes in lipid parameters by visit from baseline.• Absolute change in number of microchannels in matched segments of all lesions assessed in an individual subject as determined by OCT from baseline to week 50.• Absolute change in macrophage composition in matched segments of all lesions assessed in an individual subject as determined by OCT from baseline to week 50.• Absolute change in lipid content in matched segments of all lesions assessed in an individual subject as determined by IVUS from baseline to week 50.

The primary estimand consists of:

- The target population, which is the adult subjects with NSTEMI-ACS who are taking maximally tolerated statin therapy with or without additional lipid-modifying medication.
- The primary variable, which is the absolute change in minimum FCT in a matched segment of artery as determined by OCT from baseline to week 50.
- The summary measure, which is the mean treatment difference of the primary variable means between evolocumab and placebo.
- The intercurrent events, all randomized subjects who receive at least 1 dose of investigational product regardless of adherence to treatment.

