6.1 Inclusion Criteria

Subjects are eligible to be included in the study only if all of the following criteria apply:

- 101 Provided informed consent prior to initiation of any study-specific activities/procedures.
- 102 Age \geq 18 years at screening.
- 103 Clinical indication for coronary angiography during admission due to non-ST-segment elevation acute coronary syndrome (NSTEMI-ACS) with interventional treatment of culprit plaque.
- 104 An eligible LDL-C level via local lab assessment based on statin use at screening (see [Section 9.1.1](#)):
- No statin use: \geq 130 mg/dL
 - Low- or moderate-intensity statin use (see [Table 7-1](#)): \geq 80 mg/dL
 - High-intensity statin use (see [Table 7-1](#)): \geq 60 mg/dL
- 105 On maximally tolerated statin therapy in accordance with standard of care per local guidelines prior to randomization. See [Section 7.1.4](#) for details.
- 106 Tolerates placebo run-in injection at screening.
- 107 Meets all the following criteria at the qualifying coronary angiogram:
- Angiographic evidence of coronary artery disease (CAD) with \geq 20% reduction of lumen diameter by angiographic visual estimation, in addition to the culprit plaque.
 - Left main coronary artery must not have a $>$ 50% reduction in lumen diameter by visual angiographic estimation.
 - Targeted vessel:
 - may not be the culprit vessel for the current or a previous myocardial infarction (MI).
 - has not undergone prior percutaneous coronary intervention (PCI) or coronary artery bypass grafting (CABG), and may not be a bypass graft.
 - may not be a candidate for PCI or CABG currently or over the next 12 months, in the opinion of the investigator.
 - must be accessible by the OCT catheter.
 - Targeted segment:
 - must have up to 50% but not $>$ 50% reduction in lumen diameter by visual angiographic estimation and must be at least 40 mm in length.
 - must contain at least 1 image with a FCT of \leq 120 μ m and at least 1 image with a lipid arc of $>$ 90° as determined by the imaging core laboratory
 - distal plaques of up to 50% stenosis by visual angiographic estimation are permitted, provided that such stenosis is not a target for PCI or CABG.

Approved

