7.1.4 Other Protocol-required Therapies

All other protocol-required therapies including, background lipid-lowering therapy, that are commercially available are not provided or reimbursed by Amgen (except if required

Approved

by local regulation). The investigator will be responsible for obtaining supplies of these protocol-required therapies.

Subjects must receive maximally tolerated statin therapy with or without additional lipid-modifying medication during the study. Statin therapy must be initiated or up-titrated to the maximally tolerated dose prior to randomization for all subjects; local guidelines should be taken into consideration when determining optimal treatment. All lipid therapies (doses and regimen) should remain unchanged for the duration of study participation (up to 52 weeks). All subjects should receive high-intensity statin therapy with atorvastatin \geq 40 mg daily or equivalent (Table 7-1; criteria modified from American College of Cardiology/American Heart Association [ACC/AHA] guidelines), in accordance with local guidelines. If not receiving atorvastatin \geq 40 mg or equivalent, the investigator must attest in eCRF that higher dose statin therapy has been considered but is not appropriate for this subject (eg, dose not tolerated, dose not available in that country, other significant concern).

If making any changes to this therapy after randomization, the reason for the change must be provided in the CRF and the Amgen medical monitor or designee should be consulted before making the change.

Other regulatory-approved lipid regulating therapies (eg, ezetimibe) used at screening should remain unchanged for the duration of study participation (up to 52 weeks).

Beyond the week 52 assessment, use of statins and other lipid regulating therapies will be at the discretion of the investigator.

Table 7-1. Acceptable Background Statin Therapy

	High-intensity Statin Therapy	Moderate-intensity Statin Therapy	Low-intensity Statin Therapy
Atorvastatin	\geq 40 mg QD	10 mg to < 40 mg QD	< 10 mg QD
Rosuvastatin	\geq 20 mg QD	5 mg to < 20 mg QD	< 5 mg QD
Simvastatin ^a	\geq 80 mg QD	20 mg to < 80 mg QD	< 20 mg QD
Pravastatin	-	\geq 40 mg QD	< 40 mg QD
Lovastatin	-	\geq 40 mg QD	< 40 mg QD
Fluvastatin	-	80 mg QD	< 80 mg QD
Pitavastatin	-	\geq 2 mg QD	< 2 mg QD

QD = once daily

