9.1.1 Screening, Enrollment and/or Randomization

Informed consent must be obtained before completing any screening procedure or discontinuation of standard therapy for any disallowed therapy. After the subject has signed the informed consent form, the site will register the subject in the IVRS/IWRS and screen the subject in order to assess eligibility for participation. The screening window is up to 1 week.

All screening evaluations must be completed and reviewed to confirm that potential subjects meet all eligibility criteria, including acceptability of OCT data set as determined by the imaging core laboratory. The investigator will maintain a screening log to record details of all subjects screened and to confirm eligibility or record reasons for screening failure, as applicable.

If a subject has not met all eligibility criteria at the time of randomization, the subject will be registered as a screen fail IVRS/IWRS. Subjects cannot undergo rescreening during the same admission, (ie, index date [admission]). Rescreening is only permitted if a subject is re-admitted for new occurrence of NSTE-ACS that is not related to the NSTE-ACS at index admission. Screen fail subjects may be eligible for rescreening 2 times.

All rescreened subjects must consent. Rescreen subjects must be registered as rescreens in IVRS/IWRS. Once the subject is registered as rescreened, a new 7-day screening window will begin. With the exception of the screening placebo injection, rescreened subjects will repeat all screening procedures. Rescreened subjects will maintain the originally assigned subject identification number.

For procedures regarding LDL-C assessments during screening, these should occur between admission for NSTE-ACS and the coronary angiogram. Subject eligibility ([Section 6.1](#); inclusion criterion [104](#)) based on subjects' statin dose at the time of LDL-C blood sample measurement is as follows:

No statin use

- LDL-C: ≥ 130 mg/dL

Low- or Moderate-intensity statin dose (see [Table 7-1](#))

- LDL-C: ≥ 80 mg/dL

High-intensity statin dose (see [Table 7-1](#))

- LDL-C: ≥ 60 mg/dL

Day 1 of the treatment period (ie, first dose of investigational product) must happen within 7 days of the signing of the informed consent.

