5.3 Demographics and Baseline Related Definitions

Age

Age is the subject's age in years at enrollment as recorded on the eCRF.

Baseline Lipid and Lipid-related Parameters

Baseline values for LDL-C, triglycerides and troponin are defined as the concentrations measured through **local lab at screening**. **Baseline values for other lipids (eg, total cholesterol, HDL-C and VLDL-C), ApoA1, ApoB, Lp(a) and their derived parameters (eg, ratio between them) are defined as the concentrations measured through central lab on Study Day 1.**

Baseline Laboratory Variables

Baseline values for laboratory variables are defined as the assessment measured at screening.

Baseline Concomitant Medication Usage and Medical History

Baseline values for background statin therapy, lipid-modifying concomitant medication usage and medical history are defined as the assessment measured at screening. For concomitant medication that is not lipid-modifying baseline is defined as measurement at study day 1.

Baseline Image Data

Baseline values for OCT, IVUS image data are defined as the assessment measured at screening.

Baseline Vital Signs

Baseline values for vital signs are defined as the last non-missing value collected prior to or on Study Day 1.

Change (absolute change) from Baseline

The arithmetic difference between a post-baseline value and baseline for a given time point:

Change (absolute change) from baseline = (post-baseline value – baseline value).

Percent Change from Baseline

The percent change from baseline for a given variable at a given time point is defined as:

$100 \times [(value \text{ at given time point} - baseline \text{ value}) / baseline \text{ value}]$.

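### Is the 50.97 µm treatment effect really a change within one arm, so that the 90% power ignores the statin response on placebo?

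*Protocol*

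**What the plan says.** Protocol 10.1, repeated in SAP 3.2, uses a regression across seven historical trials: 1.4785 µm of FCT gained per 1 mg/dL of LDL-C lowered. For a 50 mg/dL reduction it predicts 73.92 µm (95% CI 50.97 to 96.88). The plan takes 50.97 µm as the treatment effect, "which is approximated from the lower bound 95% CI of the expected change in FCT from the regression model", and "based on a conservative assumption of 50 mg/dL reduction in LDL-C from baseline to week 50". It then applies a two-sided t-test at 0.05 with SD 86 µm and about 125 analysed out of 150.

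The estimand's summary measure (Protocol 4.1) is a contrast, "which is the mean treatment difference of the primary variable means between evolocumab and placebo".

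The passages on LDL-C timing are these:

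- SAP 5.3: "Baseline values for LDL-C, triglycerides and troponin are defined as the concentrations measured through" the local laboratory at screening.
- Protocol 9.1.1, on the LDL-C assessments during screening: "these should occur between admission for NSTE-ACS and the coronary angiogram".
- Protocol 6.1, criterion 104: "An eligible LDL-C level via local lab assessment based on statin use at screening", with an entry level of 130 mg/dL for patients on no statin.
- Protocol 7.1.4: "Statin therapy must be initiated or up-titrated to the maximally tolerated dose prior to randomization for all subjects".

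**The concern.** Put together, these passages suggest a mismatch. If baseline LDL-C is sampled before statins are optimised, a fall from that baseline contains a statin effect that placebo patients share. The regression that predicts an FCT gain on evolocumab would then predict one on placebo too. The protocol's own rationale supports this: "Lipid-lowering therapy with statins has proven to have beneficial effects on plaque morphology in patients suffering from coronary artery disease". The sample size section states no placebo change and subtracts none.

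The margin is thin. At 50.97 µm the design has less than 1 µm to spare before power drops below 90%. If 50.97 µm were only the evolocumab-arm gain, the real contrast would be smaller and the quoted power too high. There is also a risk of misreading later: a large LDL-C fall in the evolocumab arm could be taken to confirm the 50 mg/dL premise while the gap between arms was smaller. Finally, the plan calls 50 mg/dL conservative without saying why.

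**Working it through.** **Inputs from Protocol 10.1 and SAP 3.2.** Difference 50.97 µm, SD 86 µm, two-sided 0.05, 125 analysed (62.5 per arm), slope 1.4785 µm per mg/dL.

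**1. Reproduce the plan.** Standardised effect = 50.97 / 86 = 0.593. The two-sample t-test needs 60.8, so 61 per arm, or 122 analysed. 122 / (1 − 1/6) = 146.4, so 147 randomised, against the plan's 150. Power at 62.5 per arm is 90.8%. Exactly 90% needs 50.26 µm, which leaves 50.97 − 50.26 = 0.71 µm to spare. The arithmetic is sound.

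**2. What the regression figure can mean.** 1.4785 × 50 = 73.925, which matches the stated 73.92. The prediction is slope times 50 with no visible intercept. That fits a line through the origin applied to one arm. It fits equally well the FCT difference between two groups 50 mg/dL apart, where any intercept cancels. The arithmetic does not decide between them.

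**3. Hold evolocumab fixed and add a placebo gain (assumed values).**

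| Placebo FCT gain (µm) | Power, evolocumab gain 50.97 µm | Power, evolocumab gain 73.92 µm |
|---|---|---|
| 0 | 90.8% | 99.8% |
| 5 | 84.2% | 99.4% |
| 10 | 75.2% | 98.5% |
| 15 | 64.1% | 96.7% |
| 20 | 51.5% | 93.5% |

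The middle column looks alarming, but it combines two incompatible premises. If baseline precedes statin optimisation, the statin effect enlarges the fall in both arms. The evolocumab gain cannot stay fixed while only placebo improves.

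**4. Treat both arms alike.** Take entry at 130 mg/dL on no statin, an assumed 40% statin effect, and a 55% evolocumab effect (the low end of the placebo-adjusted range in Protocol 3.3.1.1).

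- LDL-C on statin: 130 × 0.60 = 78 mg/dL.
- Placebo fall: 130 − 78 = 52 mg/dL.
- Evolocumab fall: 130 − 78 × 0.45 = 94.9 mg/dL.
- Between-arm gap: 94.9 − 52 = 42.9 mg/dL.

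With FCT change proportional to LDL-C change, only the gap matters:

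- Slope implied by the lower limit, 50.97 / 50 = 1.0194: 42.9 × 1.0194 = 43.7 µm, power 80.5%.
- Point slope: 42.9 × 1.4785 = 63.4 µm, power 98.3%.

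The gap needed for 90% power is 50.26 / 1.0194 = 49.3 mg/dL at the lower slope and 50.26 / 1.4785 = 34.0 mg/dL at the point slope.

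**5. Is 50 mg/dL plausible as a net figure?** At the 60 mg/dL entry minimum on a high-intensity statin, reductions of 55% to 75% give 33 to 45 mg/dL; a net 50 would need 50 / 60 = 83%. At the 130 mg/dL no-statin minimum, with an assumed 30% to 50% statin effect, LDL-C on statin is 65 to 91 mg/dL. The net gap is then 65 × 0.55 = 35.8 to 91 × 0.75 = 68.3 mg/dL. These are entry minima, not expected means, so 50 mg/dL is neither confirmed nor excluded.

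**The case for a change.** The strongest case for acting is textual. Elsewhere both documents use the phrase about change from baseline to week 50 for change within a subject, and keep the language of treatment difference for the contrast between arms. The regression output is called a predicted mean increase. Read literally, then, 50 mg/dL is a fall within one arm and a placebo change is missing. The lower confidence limit covers uncertainty in the regression; nothing says it also allows for a placebo response. One sentence would settle it.

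The loose wording and the unsupported word conservative stand. The claim of a contradiction does not:

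- The sample size paragraph sets out to power an effect of evolocumab relative to placebo and labels 50.97 µm as that effect. With 50 mg/dL read as a net difference, the paragraph is consistent throughout.
- SAP 5.3 defines baseline for the analyses, and SAP 3.2 does not refer to it. The SAP's version table shows that the lipid baseline text was revised in January 2021, whereas the SAP dates the protocol to 19 April 2018. A later analysis definition cannot fix what an earlier planning assumption meant.
- SAP 5.3 says only that the value is a local one from screening. That it precedes statin optimisation is inferred from Protocol 9.1.1 and 7.1.4; Table 2-1 puts lipid testing and statin optimisation in the same screening column. Patients already at their maximally tolerated dose have nothing to up-titrate.
- Nothing in the plan says that the evolocumab-arm LDL-C fall will be judged against 50 mg/dL. The ANCOVA in SAP 9.5.3 already has a treatment term, so the between-arm LDL-C difference will be available.

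**Conclusion.** No change follows. The sentence is ambiguous about whether 50 mg/dL is a net difference or a fall within one arm, and the documents do not settle it. On the net reading the stated 90% holds (90.8% recomputed). On the other reading the shortfall cannot be sized from the documents, because it needs a placebo LDL-C or FCT change that they do not give. Treating both arms alike, the one worked case gives 80.5% at the lower-limit slope and 98.3% at the point slope. Those two figures rest on an assumed 40% statin effect, entry at the no-statin minimum and a proportional regression.

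Other choices in the calculation are cautious: the lower 95% limit in place of 73.92 µm, the top of the reported 22 to 86 µm range for the SD of change, and no credit for the baseline FCT adjustment in the primary ANCOVA. Underpowering is therefore not shown. Saying in words what 50 mg/dL means would tidy the text, but the number randomised, the estimand, the primary test, the type I error and every reported result would stay the same.
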